5.2.1.2 Dose Modification (Escalation/Titration/Other)

Adverse events (both non-serious and serious) associated with pembrolizumab exposure may represent an immunologic etiology. These adverse events may occur shortly after the first dose or several months after the last dose of treatment. Pembrolizumab must be withheld for drug-related toxicities and severe or life-threatening AEs as per 3 below. See Section 5.6 for supportive care guidelines, including use of corticosteroids.

Table 3.1 Dose Modification Guidelines for Pembrolizumab-Related Adverse Events

Toxicity	Hold Treatment For Grade	Timing for Restarting Treatment	Treatment Discontinuation
Diarrhea/ Colitis	2-3	Toxicity resolves to Grade 0-1	Toxicity does not resolve within 12 weeks of last dose or inability to reduce corticosteroid to 10 mg or less of prednisone or equivalent per day within 12 weeks
	4	Permanently discontinue	Permanently discontinue

Toxicity	Hold Treatment For Grade	Timing for Restarting Treatment	Treatment Discontinuation
AST, ALT, or Increased Bilirubin	2 (AST/ALT : 3-5 x upper limit of normal [ULN]; bilirubin: 1.5-3 x ULN)	Toxicity resolves to Grade 0-1.	Toxicity does not resolve within 12 weeks of last dose or inability to reduce corticosteroid to 10 mg or less of prednisone or equivalent per day within 12 weeks
	3-4	Permanently discontinue	Permanently discontinue
Type 1 diabetes mellitus (if new onset) or Hyperglycemia	T1DM or 3-4	Hold pembrolizumab for new onset Type 1 diabetes mellitus or Grade 3-4 hyperglycemia associated with evidence of beta cell failure	Resume pembrolizumab when patients are clinically and metabolically stable
Hypophysitis	2-4	Toxicity resolves to Grade 0-1. Therapy with pembrolizumab can be continued while endocrine replacement therapy is instituted	Toxicity does not resolve within 12 weeks of last dose or inability to reduce corticosteroid to 10 mg or less of prednisone or equivalent per day within 12 weeks
Hyperthyroidism	3	Toxicity resolves to Grade 0-1	Toxicity does not resolve within 12 weeks of last dose or inability to reduce corticosteroid to 10 mg or less of prednisone or equivalent per day within 12 weeks
	4	Permanently discontinue	Permanently discontinue
Hypo-thyroidism		Therapy with pembrolizumab can be continued while thyroid replacement therapy is instituted	Therapy with pembrolizumab can be continued while thyroid replacement therapy is instituted

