Infusion Reaction	2 ^a	Toxicity resolves to Grade 0-1	Permanently discontinue if toxicity develops despite adequate premedication
	3-4	Permanently discontinue	Permanently discontinue
Pneumonitis	2	Toxicity resolves to Grade 0-1	Toxicity does not resolve within 12 weeks of last dose or inability to reduce corticosteroid to 10 mg or less of prednisone or equivalent per day within 12 weeks
	3-4 or recurrent grade 2	Permanently discontinue	Permanently discontinue
Renal Failure or Nephritis	2	Toxicity resolves to Grade 0-1	Toxicity does not resolve within 12 weeks of last dose or inability to reduce corticosteroid to 10 mg or less of prednisone or equivalent per day within 12 weeks
	3-4	Permanently discontinue	Permanently discontinue
Myocarditis	3-4	Permanently discontinue	Permanently discontinue
Skin or suspicious Steven-Johnson syndrome (SJS) or toxic epidermal necrolysis (TEN)	3	Toxicity resolves to Grade 0-1	Toxicity does not resolve within 12 weeks of last dose or inability to reduce corticosteroid to 10 mg or less of prednisone or equivalent per day within 12 weeks

Toxicity	Hold Treatment For Grade	Timing for Restarting Treatment	Treatment Discontinuation
Skin	4	Permanently discontinue	Permanently discontinue
Confirmed SJS	3-4	Permanently discontinue	Permanently discontinue
Confirmed TEN	4	Permanently discontinue	Permanently discontinue
All Other Drug-Related Toxicity ^b	3 or Severe	Toxicity resolves to Grade 0-1	Toxicity does not resolve within 12 weeks of last dose or inability to reduce corticosteroid to 10 mg or less of prednisone or equivalent per day within 12 weeks
	Persistent 2 or 3 except endocrine dysfunction under endocrine supplement with good control; toxicity does not resolve within 12 weeks of last dose or inability to reduce corticosteroid to 10 mg or less of prednisone or equivalent per day within 12 weeks		Permanently discontinue
	Recurrent 3	Permanently discontinue	Permanently discontinue
	4	Permanently discontinue	Permanently discontinue

Note: Permanently discontinue for any severe or Grade 3 drug-related AE that recurs or any life-threatening event.

^a If symptoms resolve within one hour of stopping drug infusion, the infusion may be restarted at 50% of the original infusion rate (e.g., from 100 mL/hr to 50 mL/hr). Otherwise dosing will be held until symptoms resolve and the subject should be premedicated for the next scheduled dose; Refer to Table 4– Infusion Treatment Guidelines for further management details.

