7.2.4 Evaluating Adverse Events

An investigator who is a qualified physician will evaluate all adverse events according to the NCI Common Terminology for Adverse Events (CTCAE), version 4.0. Any adverse event which changes CTCAE grade over the course of a given episode will have each change of grade recorded on the adverse event case report forms/worksheets.

All adverse events regardless of CTCAE grade must also be evaluated for seriousness.

Table 6 Evaluating Adverse Events

An investigator who is a qualified physician, will evaluate all adverse events as to:

V4.0 CTCAE Grading	Grade 1	Mild; asymptomatic or mild symptoms; clinical or diagnostic observations only; intervention not indicated.
	Grade 2	Moderate; minimal, local or noninvasive intervention indicated; limiting age-appropriate instrumental ADL.
	Grade 3	Severe or medically significant but not immediately life-threatening; hospitalization or prolongation of hospitalization indicated; disabling; limiting self-care ADL.
	Grade 4	Life threatening consequences; urgent intervention indicated.
	Grade 5	Death related to AE
Seriousness	A serious adverse event is any adverse event occurring at any dose or during any use of Merck product that:	
	† Results in death ; or	
	† Is life threatening ; or places the subject, in the view of the investigator, at immediate risk of death from the event as it occurred (Note: This does not include an adverse event that, had it occurred in a more severe form, might have caused death.); or	
	† Results in a persistent or significant disability/incapacity (substantial disruption of one's ability to conduct normal life functions); or	
	† Results in or prolongs an existing inpatient hospitalization (hospitalization is defined as an inpatient admission, regardless of length of stay, even if the hospitalization is a precautionary measure for continued observation. (Note: Hospitalization for an elective procedure to treat a pre-existing condition that has not worsened is not a serious adverse event. A pre-existing condition is a clinical condition that is diagnosed prior to the use of a Merck product and is documented in the patient's medical history.); or	
	† Is a congenital anomaly/birth defect (in offspring of subject taking the product regardless of time to diagnosis); or	

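### For life-threatening or recurrent Grade 3 endocrine events, rows of Table 3.1 allow pembrolizumab to restart or continue, while the note under the table requires permanent discontinuation

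*Combined protocol and SAP*

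**What the plan says.** All the dosing text is in Section 5.2.1.2, Table 3.1.

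- **Hypophysitis.** One row covers three grades, and its first cells read "Hypophysitis 2-4 Toxicity resolves to Grade 0-1". The row adds: "Therapy with pembrolizumab can be continued while endocrine replacement therapy is instituted". It requires permanent discontinuation only if the toxicity fails to resolve, or the steroid dose cannot be brought down, within 12 weeks.
- **Type 1 diabetes or hyperglycemia.** "Hold pembrolizumab for new onset Type 1 diabetes mellitus or Grade 3-4 hyperglycemia associated with evidence of beta cell failure". The row then says: "Resume pembrolizumab when patients are clinically and metabolically stable". It gives no condition for permanent discontinuation.
- **Hypothyroidism.** No grade is entered. The instruction is: "Therapy with pembrolizumab can be continued while thyroid replacement therapy is instituted".
- **Note under the table.** "Permanently discontinue for any severe or Grade 3 drug-related AE that recurs or any life-threatening event". No row or class of event is exempted.
- **The one endocrine exception.** It is in the row for all other drug-related toxicity: "Persistent 2 or 3 except endocrine dysfunction under endocrine supplement with good control". It stops at Grade 3.

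Three other places bear on the point. Table 6 (Section 7.2.4) describes Grade 4 as "Life threatening consequences; urgent intervention indicated". Section 5.8 makes unacceptable adverse experiences a mandatory reason for discontinuation and defines them by reference to Section 5.2.1.2. The rechallenge entry in Table 6 requires the sponsor to approve in advance any re-exposure after a serious event that the product may have caused, in line with the dose modification guidelines.

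**The concern.** The rows and the note belong to the same table and govern the same decision. For a patient whose hypophysitis or diabetes becomes life-threatening, one line permits pembrolizumab after recovery or stabilisation and the other forbids it for good. The investigator cannot comply with both, and a monitor cannot say whether restarting or stopping was the deviation.

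This is a stopping rule for events that the protocol's own grading scale calls life-threatening, so the first stake is patient safety. The second is whether adherence can be judged at all. Safety and toxicity are a secondary objective (Section 3.2), and the recorded reasons for stopping would partly reflect which line was read.

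**Working it through.** The plan states no figure on this point and no formula applies. The check sets the texts side by side.

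**Step 1: what the note covers.** It has two clauses: (a) a severe or Grade 3 drug-related event that recurs, and (b) any life-threatening event. Table 6 links Grade 4 to clause (b).

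**Step 2: rows that name Grade 4.** Counting skin, confirmed SJS and confirmed TEN separately, eleven entries prescribe permanent discontinuation at Grade 4 and agree with the note: colitis, liver tests, hyperthyroidism, infusion reaction, pneumonitis, renal, myocarditis, skin, SJS, TEN and all other. Two entries name Grade 4 and allow restart: hypophysitis and diabetes/hyperglycemia. Hypothyroidism names no grade, so it does not exclude Grade 4.

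**Step 3: apply both texts to the same event.**

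| Event | Row | Note |
|---|---|---|
| Life-threatening Grade 4 hypophysitis | Hold, then restart at Grade 0-1; may continue with hormone replacement | Stop permanently, clause (b) |
| Life-threatening Grade 4 hyperglycemia with signs of beta cell failure, or life-threatening new-onset type 1 diabetes | Hold, then resume when stable | Stop permanently, clause (b) |
| Life-threatening hypothyroidism | Continue with thyroid replacement | Stop permanently, clause (b) |
| Drug-related Grade 3 event in any of these rows that recurs | Restart or continue; no limit on recurrence | Stop permanently, clause (a) |
| First Grade 2 or 3 event, not life-threatening | Restart or continue | Not covered, so no conflict |

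The conflict is sharpest in the first two lines, because those rows name Grade 4 themselves. It is softer for recurrence: the rows do not mention recurrence, so the note could be read as adding to them. Even so, the hypothyroidism and diabetes rows give an open instruction to continue or resume, and the note contradicts it.

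**Step 4: look for a rule that settles it.**

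- Section 5.2.1.2 does not rank rows against the note.
- The written endocrine exception covers persistent Grade 2 or 3 in a different row. It reaches neither Grade 4 nor the note.
- Section 5.6.1 covers steroids, hormone replacement and insulin for these events. It is silent on restarting pembrolizumab and refers back to Section 5.2.1.
- Section 5.8 and the rechallenge entry in Table 6 both defer to the dose modification text, so each takes over the conflict.

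**Step 5: size.** The documents give no event rate. As a scale only, one affected patient is 1/26 = 3.8% of the planned enrolment and two are 2/26 = 7.7%. There may be none.

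**The case against.** The best counter-argument is that a specific row overrides a general note. The text before the table speaks of withholding pembrolizumab for severe or life-threatening events as the table directs, so it contemplates a hold for such events. Two endocrine rows name Grade 4 and allow restart while the others do not, which looks deliberate. The note would then be a backstop. This reading is possible, but it is nowhere stated. If it were adopted, clause (b) would change nothing in the rows that name Grade 4, since all the others already stop there. The table also writes an endocrine exception where it wants one, and the note has none.

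A second argument is that the note says life-threatening and not Grade 4. Table 6 also uses the term as a seriousness criterion, meaning immediate risk of death from the event as it occurred, and asks for seriousness to be judged separately from grade. In that sense, not every Grade 4 event would trigger the note. This stands as a narrowing. An event that is life-threatening in the strict sense still meets both rules.

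A third is that re-exposure after a serious, possibly related event needs the sponsor's advance approval, so the investigator does not decide alone. That is a real safeguard. It is tied to the same guidelines, however, so it adds review without saying which line to apply.

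A reader might also infer that different sites will act differently. The documents do not support that: the sample size text (Section 8.2.1) bases enrolment on a single center. Different investigators there, or the same one at different times, could still read the table differently.

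**Conclusion.** The contradiction is real but narrow. It covers life-threatening hypophysitis, type 1 diabetes or qualifying hyperglycemia, and hypothyroidism, and drug-related Grade 3 events in those rows that recur. It rests on reading the note as written, without exception, and on Table 6 as the meaning of Grade 4.

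Three stronger readings go beyond the documents.

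- **Every Grade 4 hyperglycemia is affected.** The row is limited to new-onset type 1 diabetes or Grade 3-4 hyperglycemia with signs of beta cell failure.
- **The trial's results are compromised.** Section 8.2.2.3 summarises only the incidence and severity of toxicity, and no exposure analysis is planned. Section 10.6 lists premature terminations with reasons, so such a case would be visible. Analyses are by intention to treat (Section 8.2.3.1), and disease follow-up continues after discontinuation for reasons other than recurrence (Section 5.8). No effect on 1-year recurrence-free survival is shown.
- **One of the two rules is clinically wrong.** The documents do not settle that, and this review takes no position on it.

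Few patients are likely to be affected, though that is an assumption because no frequency is given. The point still deserves correction before further use of the table, because it concerns when to stop treatment after a life-threatening event.

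**What to change.** Reconcile the note with the hypophysitis, type 1 diabetes/hyperglycemia and hypothyroidism rows, for both the life-threatening and the recurrent Grade 3 clauses. The note can name the rows it does not cover, the rows can carry the note's rule, or one sentence can state which prevails. The same edit should say whether life-threatening in the note means Grade 4 or the seriousness criterion in Table 6. Then check that Section 5.8 and the rechallenge entry in Table 6 agree with the result. The clinical content of the rule is for the sponsor and the investigator to decide.

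The cost is a line or two of protocol wording, with no change to design, sample size or analysis.

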5.2.2 Timing of Dose Administration

5.2.2.1 Cisplatin-CRT:

- a. Cisplatin-CRT is to be started within 8-12 weeks after esophagectomy, when the patient recovers well from the operation.
- b. Cisplatin 30 mg/m², IV infusion for 60~ 120 min, weekly, for 2 weeks.
 - i. Sufficient hydration will be given at the discretion of the investigator.
 - ii. Anti-emetics such as 5-HT3 antagonists, aprepitant, steroid, and metoclopramide will be given at the discretion of the investigator.
- c. Radiotherapy: (intensity modulated radiotherapy) 180-200 cGy/fraction, once daily, 5 days a week, for a total of 10-13 fractions.
 - i. Radiotherapy will be administered by megavoltage linear accelerators (\geq 6 MV photon) using multiple fields (\geq 2) technique.
 - ii. Planning CT (CT simulation) must be done for isodose distribution and evaluation of dose-volume histogram.
 - iii. The target volumes of radiation should encompass the tumor volume (both primary esophageal tumor and metastatic lymphadenopathy) with adequate margins covering subclinical disease (including submucosal, mediastinal, and/or supraclavicular or celiac lymphatics) and treatment variability (including setup errors, breathing, and organ motion). Gross tumor volume (GTV) is defined as the volume of all visible esophageal tumor and involved lymphadenopathy using all available imaging studies including CT scan, EUS, and 18F-FDG-PET scan. The clinical target volume (CTV) is defined as the

GTV plus areas considered at significant risk of microscopic disease including a 0.5-1.0cm circumferential margin and 3-4 cm longitudinal margin.

- iv. Radiation will be delivered with intensity modulated radiotherapy technique, with a daily fraction size of 180-200 cGy, 5 days a week.

5.2.2.2 Pembrolizumab:

- a. Pembrolizumab is to be started within 4 weeks after completing last dose of CRT, when the patient recovers well from the CRT.
- b. Pembrolizumab should be administered on Day 1 of each cycle after all procedures/assessments have been completed as detailed on the Trial Flow Chart (Section 6.0). Trial treatment may be administered up to 3 days before or after the scheduled Day 1 of each cycle due to administrative reasons.
- c. Pembrolizumab will be administered on an outpatient basis.
- d. Pembrolizumab 200 mg will be administered as a 30 minute IV infusion every 3 weeks. Sites should make every effort to target infusion timing to be as close to 30 minutes as possible. However, given the variability of infusion pumps from site to site, a window of -5 minutes and +10 minutes is permitted (i.e., infusion time is 30 minutes: -5 min/+10 min).
- e. The Pharmacy Manual contains specific instructions for the preparation of the pembrolizumab infusion fluid and administration of infusion solution.

5.2.2.3 Visits during adjuvant therapy (also listed in 7.1.5.2):

- a. During the period of adjuvant cisplatin-CRT:
 - i. The patient will be seen on a weekly basis until 2 weeks after completing CRT.
 - ii. The patient will be evaluated for clinical symptoms and signs, hemogram, and biochemistry panel including bilirubin, AST, ALT, BUN, creatinine, Na, K, Ca, Mg, and other abnormalities found at screening check.
- b. During the period of adjuvant pembrolizumab therapy:
 - i. The patient will be seen on a 3-weekly basis for a total of 54 weeks.
 - ii. The patient will be evaluated for clinical symptoms and signs, hemogram, and biochemistry panels including bilirubin, AST, ALT, ALP, gamma-GT, LDH, albumin, BUN, creatinine, Na, Cl, K, Ca, Mg, glucose, and endocrine function (every 2 cycles) including TSH, T3, fT4, ACTH and cortisol.
 - iii. Pregnancy Test – Urine or Serum beta-HCG (for woman only), coagulation

test with PT/INR and aPTT, and urinalysis will be checked every 2 cycles.

5.2.3 Trial Blinding/Masking

This is an open-label trial; therefore, the Sponsor, investigator and subject will know the treatment administered.

5.3 Randomization or Treatment Allocation

This is a single-arm study.

5.4 Stratification

No stratification will be done

5.5 Concomitant Medications/Vaccinations (allowed & prohibited)

Medications or vaccinations specifically prohibited in the exclusion criteria are not allowed during the ongoing trial. If there is a clinical indication for one of these or other medications or vaccinations specifically prohibited during the trial, discontinuation from trial therapy or vaccination may be required. The investigator should discuss any questions regarding this with the Merck Clinical team. The final decision on any supportive therapy or vaccination rests with the investigator and/or the subject's primary physician.

5.5.1 Acceptable Concomitant Medications

All treatments that the investigator considers necessary for a subject's welfare may be administered at the discretion of the investigator in keeping with the community standards of medical care. All concomitant medication will be recorded on the case report form (CRF) including all prescription, over-the-counter (OTC), herbal supplements, and IV medications and fluids. If changes occur during the trial period, documentation of drug dosage, frequency, route, and date may also be included on the CRF.

All concomitant medications received within 28 days before the first dose of trial treatment and 30 days after the last dose of trial treatment should be recorded. Concomitant medications administered after 30 days after the last dose of trial treatment should be recorded for SAEs and ECIs as defined in Section 7.2.

5.5.2 Prohibited Concomitant Medications

Subjects are prohibited from receiving the following therapies during the Screening and Treatment Phase (including retreatment for post-complete response relapse) of this trial:

- Antineoplastic systemic biological therapy not specified in this protocol
- Immunotherapy not specified in this protocol

- Chemotherapy not specified in this protocol
- Investigational agents other than pembrolizumab
- Radiation therapy not specified in this protocol
- Live vaccines within 30 days prior to the first dose of trial treatment and while participating in the trial. Examples of live vaccines include, but are not limited to, the following: measles, mumps, rubella, varicella/zoster, yellow fever, rabies, BCG, and typhoid vaccine.
- Systemic glucocorticoids for any purpose other than to modulate symptoms from an event of clinical interest of suspected immunologic etiology. The use of physiologic doses of corticosteroids may be approved after consultation with the Sponsor.

Subjects who, in the assessment by the investigator, require the use of any of the aforementioned treatments for clinical management should be removed from the trial. Subjects may receive other medications that the investigator deems to be medically necessary.

The Exclusion Criteria describes other medications which are prohibited in this trial.

There are no prohibited therapies during the Post-Treatment Follow-up Phase.

5.6 Rescue Medications & Supportive Care

5.6.1 Supportive Care Guidelines

Subjects should receive appropriate supportive care measures as deemed necessary by the treating investigator. Suggested supportive care measures for the management of adverse events with potential immunologic etiology are outlined below. Where appropriate, these guidelines include the use of oral or intravenous treatment with corticosteroids as well as additional anti-inflammatory agents if symptoms do not improve with administration of corticosteroids. Note that several courses of steroid tapering may be necessary as symptoms may worsen when the steroid dose is decreased. For each disorder, attempts should be made to rule out other causes such as metastatic disease or bacterial or viral infection, which might require additional supportive care. The treatment guidelines are intended to be applied when the investigator determines the events to be related to pembrolizumab.

Note: if after the evaluation the event is determined not to be related, the investigator does not need to follow the treatment guidance (as outlined below). Refer to Section 5.2.1 for dose modification.

It may be necessary to perform conditional procedures such as bronchoscopy, endoscopy, or skin photography as part of evaluation of the event.

- **Pneumonitis:**
 - For **Grade 2 events**, treat with systemic corticosteroids. When symptoms improve to Grade 1 or less, steroid taper should be started and continued over no less than 4 weeks.

- For **Grade 3-4 events**, immediately treat with intravenous steroids.
Administer additional anti-inflammatory measures, as needed.
- Add prophylactic antibiotics for opportunistic infections in the case of prolonged steroid administration.
- **Diarrhea/Colitis:**

Subjects should be carefully monitored for signs and symptoms of enterocolitis (such as diarrhea, abdominal pain, blood or mucus in stool, with or without fever) and of bowel perforation (such as peritoneal signs and ileus).

 - All subjects who experience diarrhea/colitis should be advised to drink liberal quantities of clear fluids. If sufficient oral fluid intake is not feasible, fluid and electrolytes should be substituted via IV infusion. For Grade 2 or higher diarrhea, consider GI consultation and endoscopy to confirm or rule out colitis.
 - For **Grade 2 diarrhea/colitis**, administer oral corticosteroids.
 - For **Grade 3 or 4 diarrhea/colitis**, treat with intravenous steroids followed by high dose oral steroids.
 - When symptoms improve to Grade 1 or less, steroid taper should be started and continued over no less than 4 weeks.
- **Type 1 diabetes mellitus (if new onset, including diabetic ketoacidosis [DKA]) or \geq Grade 3 Hyperglycemia, if associated with ketosis (ketonuria) or metabolic acidosis (DKA)**
 - For **T1DM or Grade 3-4 Hyperglycemia**
 - Insulin replacement therapy is recommended for Type I diabetes mellitus and for Grade 3-4 hyperglycemia associated with metabolic acidosis or ketonuria.
 - Evaluate patients with serum glucose and a metabolic panel, urine ketones, glycosylated hemoglobin, and C-peptide.
- **Hypophysitis:**
 - For **Grade 2 events**, treat with corticosteroids. When symptoms improve to Grade 1 or less, steroid taper should be started and continued over no less than 4 weeks. Replacement of appropriate hormones may be required as the steroid dose is tapered.
 - For **Grade 3-4 events**, treat with an initial dose of IV corticosteroids followed by oral corticosteroids. When symptoms improve to Grade 1 or less, steroid taper should be started and continued over no less than 4 weeks. Replacement of appropriate hormones may be required as the steroid dose is tapered.
- **Hyperthyroidism or Hypothyroidism:**

Thyroid disorders can occur at any time during treatment. Monitor patients for changes in thyroid function (at the start of treatment, periodically during treatment,

and as indicated based on clinical evaluation) and for clinical signs and symptoms of thyroid disorders.

- **Grade 2** hyperthyroidism events (and **Grade 2-4** hypothyroidism):
 - In hyperthyroidism, non-selective beta-blockers (e.g. propranolol) are suggested as initial therapy.
 - In hypothyroidism, thyroid hormone replacement therapy, with levothyroxine or liothyroinine, is indicated per standard of care.
- **Grade 3-4** hyperthyroidism
 - Treat with an initial dose of IV corticosteroid followed by oral corticosteroids. When symptoms improve to Grade 1 or less, steroid taper should be started and continued over no less than 4 weeks. Replacement of appropriate hormones may be required as the steroid dose is tapered.
- **Hepatic:**
 - For **Grade 2** events, monitor liver function tests more frequently until returned to baseline values (consider weekly).
 - Treat with IV or oral corticosteroids
 - For **Grade 3-4** events, treat with intravenous corticosteroids for 24 to 48 hours.
 - When symptoms improve to Grade 1 or less, a steroid taper should be started and continued over no less than 4 weeks.
- **Renal Failure or Nephritis:**
 - For **Grade 2** events, treat with corticosteroids.
 - For **Grade 3-4** events, treat with systemic corticosteroids.
 - When symptoms improve to Grade 1 or less, steroid taper should be started and continued over no less than 4 weeks.
- **Management of Infusion Reactions:** Signs and symptoms usually develop during or shortly after drug infusion and generally resolve completely within 24 hours of completion of infusion.

Table 4 below shows treatment guidelines for subjects who experience an infusion reaction associated with administration of pembrolizumab (MK-3475).

Table 4 Infusion Reaction Treatment Guidelines

NCI CTCAE Grade	Treatment	Premedication at subsequent dosing
Grade 1 Mild reaction; infusion interruption not indicated; intervention not indicated	Increase monitoring of vital signs as medically indicated until the subject is deemed medically stable in the opinion of the investigator.	None
Grade 2 Requires infusion interruption but	Stop Infusion and monitor symptoms. Additional appropriate medical therapy may	Subject may be premedicated 1.5h (\pm 30 minutes) prior to infusion of

NCI CTCAE Grade	Treatment	Premedication at subsequent dosing
responds promptly to symptomatic treatment (e.g., antihistamines, NSAIDS, narcotics, IV fluids); prophylactic medications indicated for <=24 hrs	include but is not limited to: IV fluids Antihistamines NSAIDS Acetaminophen Narcotics Increase monitoring of vital signs as medically indicated until the subject is deemed medically stable in the opinion of the investigator. If symptoms resolve within one hour of stopping drug infusion, the infusion may be restarted at 50% of the original infusion rate (e.g., from 100 mL/hr to 50 mL/hr). Otherwise dosing will be held until symptoms resolve and the subject should be premedicated for the next scheduled dose. Subjects who develop Grade 2 toxicity despite adequate premedication should be permanently discontinued from further trial treatment administration.	pembrolizumab (MK-3475) with: Diphenhydramine 50 mg po (or equivalent dose of antihistamine). Acetaminophen 500-1000 mg po (or equivalent dose of antipyretic).
Grades 3 or 4 Grade 3: Prolonged (i.e., not rapidly responsive to symptomatic medication and/or brief interruption of infusion); recurrence of symptoms following initial improvement; hospitalization indicated for other clinical sequelae (e.g., renal impairment, pulmonary infiltrates) Grade 4: Life-threatening; pressor or ventilatory support indicated	Stop Infusion. Additional appropriate medical therapy may include but is not limited to: IV fluids Antihistamines NSAIDS Acetaminophen Narcotics Oxygen Pressors Corticosteroids Epinephrine Increase monitoring of vital signs as medically indicated until the subject is deemed medically stable in the opinion of the investigator. Hospitalization may be indicated. Subject is permanently discontinued from further trial treatment administration.	No subsequent dosing
Appropriate resuscitation equipment should be available in the room and a physician readily available during the period of drug administration.		

